10.1.10.2 Glomerular Filtration Rate

Measured GFR determined using the FAST VFI Technology will be compared to the mGFR determined using the Iohexol clearance test for Cohorts 2 through 4 only. The results will be listed by subject and summarized by presenting descriptive statistics for each cohort.

Correlation analysis will be done for comparing the GFR measurement determined using FAST VFI and mGFR technology with Iohexol clearance. Pearson correlation coefficient, standard error and 95% confidence interval for coefficient will be provided. In addition scatter plot will be provided for the GFR and mGFR measurements for Cohorts 2 through 4.

In addition, Bland-Altman plots will be created to compare the FAST VFI results to the mGFR determined using the Iohexol clearance test in each of the cohorts.

Additionally, Estimated GFR calculated using the MDRD, CKD-EPI and Cockcroft-Gault equations will be listed by subject and summarized by presenting descriptive statistics for each cohort (Cohorts 1 through 4).

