6.1.3 Randomization and Treatment Assignments

This is an open-label study. Eligible subjects/patients will be enrolled in a cohort based on renal function and will be assigned sequential subject numbers.

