10.1.10 Analysis of Pharmacodynamic Data

10.1.10.1 Plasma Volume (PV)

The FAST PV Technology plasma volume (PV) will be compared to PV estimated using Nadler's formula. Plasma volume data will be listed and summarized by presenting descriptive statistics of raw data and for change in plasma volume.

Correlation analysis will be done for comparing the PV measured using FAST PV method and PV estimated using Nadler's Formula for each cohorts. Pearson product-moment correlation coefficient, standard error with 95% confidence interval of the coefficient will be provided.

In addition scatter plot will also be provided to support the correlation analysis. Also, histogram will be provided for the magnitude of difference (PV using FAST PV - PV estimated using Nadler's formula).

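### The FAST-versus-iohexol GFR correlation has no cohort split, so as written a high r over Cohorts 2 to 4 would be weak evidence of individual-level agreement

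*SAP*

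**What the plan says.** SAP 10.1.10.2 states that FAST GFR will be "compared to the mGFR determined using the Iohexol clearance test for Cohorts 2 through 4 only". It continues: "Correlation analysis will be done for comparing the GFR measurement determined using FAST VFI and mGFR technology with Iohexol clearance", and "Pearson correlation coefficient, standard error and 95% confidence interval for coefficient will be provided". The accompanying figure is described in these words: "scatter plot will be provided for the GFR and mGFR measurements for Cohorts 2 through 4".

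None of the correlation wording mentions a split by cohort, and Protocol 10.5.2 adds none. Elsewhere the SAP names the split when it wants one. In 10.1.10.1 the plasma-volume correlation is between FAST PV and "PV estimated using Nadler's Formula for each cohorts". In 10.1.10.2 the GFR descriptive statistics are by cohort, and the Bland-Altman plots compare FAST with the "mGFR determined using the Iohexol clearance test in each of the cohorts".

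On how the cohorts are formed, SAP 6.1.3 says "Eligible subjects/patients will be enrolled in a cohort based on renal function". The bands in SAP 6.1.1 are eGFR 60 or more (Cohort 2), 30 to below 60 (Cohort 3) and 15 to below 30 mL/min/1.73 m² (Cohort 4), with up to 8 people in each. Protocol 6.1 bases them on the CKD-EPI creatinine equation.

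**The concern.** A correlation depends on the spread of the sample as well as on how well two methods agree. Here the design fixes much of the spread: three groups are chosen from adjoining eGFR bands before VFI is given. Pooled over the three, r will be high for any method that separates the groups, even if it says nothing about who is higher or lower within a group.

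Comparing FAST with iohexol GFR is a stated secondary objective, and correlation is one of only two methods named for it, with Bland-Altman plots. Neither SAP 10.1.10.2 nor the output list in SAP 11 names a tabulated mean difference or limits of agreement. That leaves r as the only listed estimate with an interval for this comparison, and a reader of the study report could take a high value as showing agreement in individuals.

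**Working it through.** The documents give no expected r, agreement target or power figure, so there is no stated number to reproduce. The check asks what pooled r a method would give if it carried only cohort information.

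**Inputs from the documents.** The three eGFR bands; at most 3 × 8 = 24 people; Pearson r with a 95% CI.

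**Assumptions.** The documents give no GFR distribution, no upper limit for Cohort 2, and no scatter of measured GFR around eGFR. I took GFR as uniform within each band, the top of Cohort 2 between 90 and 140, and extra scatter with CV 0 to 30%.

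**Closed form.** Let B be the variance between cohort means and W the average variance within cohorts. A method returning an independent random value from the right cohort has r = B/(B + W). One returning only the cohort mean has r = √[B/(B + W)].

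With Cohort 2 at 60 to 120:
- The cohort means are 90, 45 and 22.5, averaging 52.5. B = (37.5² + 7.5² + 30²)/3 = 787.5.
- W = (60²/12 + 30²/12 + 15²/12)/3 = (300 + 75 + 18.75)/3 = 131.25.
- No extra scatter: r = 787.5/918.75 = 0.86.
- CV 20%: the mean of (cohort mean² + variance) is 3,675, and 0.04 × 3,675 = 147. W = 278.25 and r = 787.5/1,065.75 = 0.74.
- CV 30%: 0.09 × 3,675 = 330.75. W = 462 and r = 787.5/1,249.5 = 0.63.

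Over all upper limits from 90 to 140, the random-value method gives r of 0.73 to 0.89 for CV 0 to 20%, and 0.60 to 0.64 at CV 30%. The cohort-mean method gives 0.78 to 0.94 over CV 0 to 30%.

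**Interval.** Fisher z gives tanh(atanh r ± 1.96/√(n − 3)). At n = 24 the half-width is 1.96/√21 = 0.428, so zero is excluded once r exceeds tanh(0.428) = 0.403. At r = 0.60 the CI is 0.26 to 0.81. In simulation of the random-value method, the CI excluded zero in at least 99.9% of trials for CV 0 to 20%, and in about 94 to 96% at CV 30%.

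**Comparison with a correct method.** I simulated 8 per cohort, with the same log-scale error SD on both methods and four sets of GFR limits: Cohort 2 at 60–90, 60–120 or 60–140, and one overlapping set (50–130, 22–72, 10–40). The cohort-adjusted r centres log GFR within cohort. Its Fisher half-width is 1.96/√(24 − 2 − 3) = 1.96/√19. Entries are the range of medians over the four sets.

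| Error SD | Pooled r, cohort information only | Pooled r, correct method | Cohort-adjusted r, correct method |
|---|---|---|---|
| 8% | 0.73–0.88 | 0.97–0.98 | 0.84–0.95 |
| 15% | 0.70–0.82 | 0.91–0.94 | 0.59–0.84 |
| 20% | 0.66–0.77 | 0.84–0.90 | 0.44–0.74 |

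With cohort information only, the pooled CI excluded zero in at least 97.5% of trials in every row. The cohort-adjusted r was about 0.00, with its CI above zero in about 3%.

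**Separate coefficients.** At n = 8 the half-width is 1.96/√5 = 0.877, so a single-cohort r must exceed tanh(0.877) = 0.705 before its CI excludes zero. Three separate coefficients would be very imprecise.

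**The case against.** **The pooled reading is inferred.** The SAP never uses the word, and naming Cohorts 2 to 4 may only identify who receives iohexol. This stands as a caution. The contrast with the explicit by-cohort wording nearby makes one coefficient the natural reading, and the text at least needs to settle it.

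**Pooled r is not empty.** A reader might infer that it does not depend on whether FAST ranks individuals correctly. The figures do not support that. With Cohort 2 at 60 to 120 and 8% error, 95% of trials fall in 0.73 to 0.94 with cohort information only and 0.95 to 0.99 for a correct method, with no overlap. At 15% error the ranges overlap (0.64 to 0.92 against 0.85 to 0.97). FAST also takes no creatinine or cohort input; Protocol 3.3 derives it from FD001 decay and FD003 plasma volume. Separating the cohorts is therefore real, if coarse, evidence of measurement.

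**The study is descriptive.** Protocol 3.7 sets no formal hypothesis, there is no threshold on r, and no decision depends on its CI excluding zero. A reader might also infer that the trial aims to show that FAST adds to creatinine equations. The objectives say only that the methods will be compared, and Protocol 3.2 presents the test as an adjunct.

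**Other planned output would show a failure.** With Cohort 2 at 60 to 120 and 8% error, the half-widths of the limits of agreement are about 50, 25 and 13 mL/min in Cohorts 2, 3 and 4 with cohort information only, against about 19, 10 and 5 for a correct method. The per-cohort plots would reveal this. It stands, and is the main reason the point is modest.

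**The adjusted r has its own range problem.** Narrow bands depress it. In the table a correct method falls as low as 0.44 at 20% error, so it should not replace the pooled r as a lone headline.

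**Conclusion.** The point holds as a modest one. As written, SAP 10.1.10.2 reads as one Pearson r over cohorts chosen from non-overlapping eGFR bands. A method carrying only cohort information would give roughly 0.6 to 0.9 with a CI that nearly always excludes zero, against about 0.84 to 0.98 for a correct method at 8 to 20% error. These ranges touch, and no benchmark is planned to tell them apart, so a high pooled r is weak evidence of individual-level agreement.

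The figures rest on assumed GFR spreads and error; the documents supply neither. They also assume 24 people, which is a maximum. With 18, at CV 30%, the random-value method's CI excludes zero in about 86 to 90% of trials. The direction does not change over the range tried.

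The documents do not support calling the GFR comparison invalid, since the by-cohort Bland-Altman plots and descriptive statistics already address agreement within cohorts.

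**What to change.** In SAP 10.1.10.2:
- State that the pooled Pearson r covers Cohorts 2 to 4, and label it as including the between-cohort spread set by eGFR selection.
- Beside it, report the partial Pearson correlation of log FAST GFR with log iohexol GFR, adjusted for cohort. Give a Fisher-z 95% CI with standard error 1/√(n − 5), which allows for the two cohort terms.
- Tabulate the mean difference and limits of agreement by cohort from the planned Bland-Altman plots, and name these as the main measure of agreement.
- Mark cohorts by symbol in Figure 14.2.3.2.

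The cost is SAP wording, one or two lines of correlation output and a short table; no new data, visits or participants. The adjusted r will be lower than the pooled one and its CI wider, because the bands restrict range. For a correct method expect about 0.84 to 0.95 at 8% error, 0.59 to 0.84 at 15% and 0.44 to 0.74 at 20%. The text should therefore say that it is read together with the limits of agreement.

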10.1.11 Analysis of Safety Data

10.1.11.1 General

All safety analyses will be performed using the Safety Population.

10.1.11.2 Adverse Events

All AEs will be coded to system organ class (SOC) and preferred term (PT) using Medical Dictionary for Regulatory Activities (MedDRA Version 20.0 or higher) and presented by subject in data listings.

Adverse events with onset on or after the first dose of study drug, or with an onset before the first dose of study drug that increase in severity on or after the first dose of study drug, will be considered treatment-emergent.

The overall incidence of TEAEs (number and percentage of subjects) as well as the number of events will be summarized by cohort (and overall), mild, moderate or severe TEAE, serious TEAE, possibly or probably related TEAE, TEAEs leading to study drug discontinuation, and serious TEAEs resulting in death.

The TEAEs will be summarized and tabulated at both the subject (number [%] of subjects) and event (number of events) level:

- By cohort, SOC, and PT
- By cohort, SOC, PT, and maximum reported severity
- By cohort, SOC, PT, and maximum relationship to study drug

For the incidence at the subject level by SOC and PT, if a subject experiences more than 1 event within the same SOC and PT, only one occurrence will be included in the incidence.

For the incidence at the subject level by SOC, PT, and severity, if a subject experiences more than one event within the same SOC and PT, only the most severe occurrence will be included in the incidence.

For the incidence at the subject level by SOC, PT and relationship to study drug; if a subject experiences more than one event within the same SOC and PT, only the most closely related occurrence will be included in the incidence.

Any SAEs, AEs with outcome of death, or AEs resulting in discontinuation of study or study drug will be listed separately.

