#### **10.6 Safety Analysis**

Electrocardiogram, vital signs, pulse oximetry, and clinical laboratory test data (observed and change from baseline) will be summarized by cohort, time point, and treatment using appropriate descriptive statistics. Physical examination findings will be listed only.

The number and percentage of subjects reporting any TEAE will be tabulated by system organ class and preferred term, cohort, and treatment (coded using Medical Dictionary for Regulatory Activities). Treatment-emergent AEs will be further classified by severity and relationship to treatment.

CONFIDENTIAL

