5 STUDY OBJECTIVES AND ENDPOINTS

5.1 Primary Objective

- To assess the safety and tolerability of VFI (employing the FAST plasma volume [PV] and measured glomerular filtration rate [mGFR] Technology) compared to Iohexol (employing Iohexol clearance methods) in healthy subjects and patients with impaired renal function
- To evaluate the PK of 5 kD carboxymethyl dextran (FD001) and 150 kD carboxymethyl dextran (FD003) in healthy subjects and patients with impaired renal function
- To evaluate the PK of FD001 and FD003 in healthy subjects receiving 2 doses of visible fluorescent injectate (VFI) separated by 24 hours to evaluate the reproducibility of the FAST mGFR Technology

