10.1.11.3 Clinical Laboratory Assessments

Clinical laboratory results will be included in the reporting of this study for hematology, coagulation, serum chemistry and urinalysis.

Absolute and change from baseline for each parameter of continuous clinical laboratory values (chemistry, hematology and urinalysis) will be summarized by cohort at each visit.

The baseline laboratory test results for clinical assessment for a particular test will be defined as the last measurement prior to the initial dose of study drug. Any unscheduled measurements will only be displayed in the listings

Other laboratory tests such as urine drugs of abuse, serology tests & pregnancy test and follicle-stimulating hormone (FSH) will also be displayed in listings.

Laboratory data will be listed by subject at each visit. Clinical laboratory values that are outside of the normal ranges values will be flagged in the data listing. Clinical significance will be indicated in the data listing.

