10.1.11.4 Vital Signs

Vital signs data including pulse oximetry will be listed by subject at each visit and time point. Absolute and change from baseline vital signs values will be summarized by cohort at each visit and time point. Any unscheduled measurements will only be displayed in the listings.

Clinical significance will be indicated in the data listing. Out of range vital signs values will be flagged in the data listing.

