10.1.11.5 Electrocardiograms

Electrocardiogram data will be listed by subject at each visit and time point.

Observed value and change from baseline of ECG parameters (HR, RR, PR, QRS, and QT and QT interval corrected for HR using Fridericia's formula (QTcF) intervals) will be summarized by cohort at each nominal timepoint. Any unscheduled measurements will only be displayed in the listings. Clinical significance will be indicated in the data listing.

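### No planned adverse-event summary table separates events that began after VFI alone from those that began after VFI plus iohexol in Cohorts 2 to 4

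*SAP*

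**What the plan says.** The first primary objective, in Protocol 4.1 and SAP 5.1, is the safety and tolerability of VFI "compared to Iohexol (employing Iohexol clearance methods) in healthy subjects and patients with impaired renal function". Adverse events are a primary endpoint.

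Protocol 10.6, and the synopsis in the same terms, has TEAEs "tabulated by system organ class and preferred term, cohort, and treatment", then classified by severity and relationship.

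SAP 10.1.11.2 states: "The overall incidence of TEAEs (number and percentage of subjects) as well as the number of events will be summarized by cohort (and overall". The SOC and preferred-term tables are also by cohort, including the one described as "By cohort, SOC, PT, and maximum relationship to study drug". An event counts as treatment-emergent from the first dose of study drug. No rule assigns it to a later agent. Tables 14.3.1.1 to 14.3.1.4 in SAP 11 are an overall summary and tables by SOC and preferred term, severity, and relationship. None splits by treatment or dosing period.

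Under Protocol 5.1, Cohorts 2 to 4 receive VFI and then iohexol 160 minutes later. Cohort 2 also receives a second VFI dose at 24 hours. Cohort 1 receives VFI and then albumin.

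**The concern.** A single cohort column in Cohorts 2 to 4 pools events that began when only VFI had been given with events that began after both agents. The relationship table does not help, because Protocol 9.2.3 asks about study drug as a whole. A reader who wants to know whether a reaction preceded iohexol must rebuild the sequence from the by-subject adverse-event and dosing listings (16.2.7.1 and 16.2.5.1).

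This matters most for acute reactions. Protocol 3.3 and 3.6.2 single out rare anaphylaxis with dextran products, with acute onset, as a reason for caution. For such events, onset before or after iohexol is the informative fact, and the summary tables would not show it.

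**Working it through.** **1. Subjects affected.** The plan's own figure reproduces: 4 cohorts × 8 = 32. Three cohorts receive both agents: 3 × 8 = 24, and 24/32 = 75%.

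**2. Does the conclusion depend on what *treatment* means?**
- *Treatment as cohort regimen.* Protocol 7.4 and SAP 6.1.3 discuss treatment assignment only as enrolment into a cohort by renal function, and each cohort has one planned regimen. Cohort by treatment then collapses to cohort, and the SAP tables meet Protocol 10.6. There is no onset split.
- *Treatment as agents received by onset.* The SAP tables lack the factor. There is no onset split.

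The gap in the tables is the same on both readings.

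**3. Length of the VFI-only period.**
- Cohorts 3 and 4, followed to 480 h: 160/(480 × 60) = 160/28,800 = 0.56%.
- Cohort 2, taking the 480 h visit as counted from dose 2 (24 + 480 = 504 h): 160/(504 × 60) = 160/30,240 = 0.53%.

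A before/after split can therefore inform only on events with rapid onset.

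**4. A longer view in Cohort 2.** Iohexol is given on Day 1 only (Protocol Table 2.2, note k). From 160 min to 24 h after a VFI dose is 1,440 − 160 = 1,280 min = 21.3 h on each day. Note c to Table 2.5 allows dose 2 at 24 h ± 1 h. If dose 2 is given at 23 h, a window fixed to end at 24 h runs 1 h past it. Ending at dose 2 gives 1,380 − 160 = 1,220 min = 20.3 h. The Day 1 window must therefore close at the earlier of 24 h and the actual time of dose 2.

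**5. Carry-over into Day 2 of Cohort 2 (healthy subjects).** Fraction left at 24 h = 2^(−24/half-life), a single-exponential approximation.
- FD003, half-lives 47 to 111 h (Protocol 3.4.2): 0.702 to 0.861. At 90 h (healthy subjects, Protocol 3.4.3): 0.831.
- FD001, half-life 5.64 h (preserved function, Protocol 3.4.3): 0.052. This is rough, because FD001 declines multi-exponentially.
- Iohexol: Protocol 3.5 has about 90% or more excreted within 24 h, so about 10% or less remains then. That point falls 160 min after dose 2 nominally, or 100 to 220 min after it within the ± 1 h allowance.

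**6. Precision.** The upper two-sided 95% exact limit with zero events is 1 − 0.025^(1/n). For n = 8 it is 36.9%; for n = 24 it is 14.2%.

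**The case against.** The strongest reply is that the SAP may already do what the protocol asks. If *treatment* means the cohort regimen, the protocol phrase is redundant. SAP 10.1.9 lends some support: it summarises PK parameters by cohort and analyte and then by treatment, as if the terms were interchangeable. This stands, and the point does not rest on the wording mismatch.

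A reader might infer an undeclared departure from the protocol, since SAP 7 lists only the change to Nadler's formula. The documents do not support that. SAP 4 and 7 refer to protocol Version 1.0, which is not available here, so the difference can be shown only against Version 1.1.

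A reader might also extend the point to other safety data, because Protocol 10.6 says that ECG, vital sign and laboratory data "will be summarized by cohort, time point, and treatment using appropriate descriptive statistics". That does not hold up as a further gap:
- Vital signs "will be summarized by cohort at each visit and time point" and ECGs "will be summarized by cohort at each nominal timepoint". Those times run from VFI, so values at 15 to 60 min are already separate from values at 170 min onward, and the 15 min ECG precedes iohexol.
- Laboratory data "will be summarized by cohort at each visit". The first scheduled postdose sample is at 480 min or later, so there is no pre-iohexol postdose value to separate.

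On the remedy, it is fair to say that listings allow inspection of what may be few events, that the study is descriptive, and that no table can isolate iohexol. Listings are a partial substitute, but they leave a summary of a primary endpoint to the reader. Comparing the Cohort 1 and Cohort 2 columns does not fill the gap either, since albumin and the second VFI dose also differ between them.

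**Conclusion.** The point stands in a limited form, as an improvement the SAP should make. Whatever *treatment* means, no planned adverse-event summary table separates onset after VFI alone from onset after VFI plus iohexol, for up to 24 of 32 subjects and a primary endpoint tied to a comparative objective.

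A reader might infer that an onset table would deliver the VFI-versus-iohexol comparison. It would not. No subject receives iohexol alone, the order is fixed, the VFI-only period is 160 min, and Day 2 in Cohort 2 begins with roughly 70% to 86% of FD003 still present and possibly some iohexol. With at most 8 subjects per cohort, even a zero count is compatible with a rate of about 37%. The gain is a clear descriptive display, chiefly for acute events.

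Confidence is moderate. The absence of the split is plain in the text. Reading *treatment* as agents received by onset is a proposal, because the protocol does not define the term.

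**What to change.** In SAP 10.1.11.2, define *treatment* for TEAEs as the agents received by the onset of the event. Add one descriptive table by SOC and preferred term, within cohort and by onset period, with the number exposed in each period as denominator:
- after VFI dose 1 and before the next agent;
- after albumin (Cohort 1);
- after iohexol, labelled as VFI plus iohexol (Cohorts 2 to 4), ending in Cohort 2 at the actual time of VFI dose 2;
- after VFI dose 2 (Cohort 2).

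Any Day 1 versus Day 2 view in Cohort 2 should use actual dosing times and start 160 min after each VFI dose. It should close at 24 h, or on Day 1 at dose 2 if that comes sooner. State the limits given in the verdict beside the table.

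Confirm that the date and clock time of onset are captured. Protocol 9.1 does not list them, and a date alone would not do, because both agents are given on Day 1. Update the SAP to cite the current protocol version.

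The cost is SAP wording, one table with sparse cells, and modest programming. Dosing times are already recorded (Protocol 7.5), and SAP 10.1.5 already counts subjects given VFI, iohexol and albumin. A count for the second VFI dose would have to be added. If the eCRF lacks onset time, the cost rises.
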